8.3.17 Clinical Global Impression of Improvement (CGI-I)

The CGI-I is evaluated by the Investigators on a 4-point scale (remission, improved, no change, worsened) based on changes from the Baseline findings of PSO.

Frequency tables by visit and by randomized treatment group for the Initial Period as well as by visit and by maintenance treatment group for the Maintenance Period will be provided for the results of the Investigator’s assessment based on the CFAS on Observed case data and NRI imputed data. Within NRI imputation, missing values are imputed with the category “No Change”.

A line plot will be generated to present change from Baseline in CGI-I score by randomized treatment group through Week 24/52.

8.3.18 Global Improvement Score for Pustular PSO

The analysis will be based on the Generalized Pustular PSO Set (GPPS). The Global Improvement Score is evaluated by the Investigators as “very much improved,” “much improved,” “minimally improved,” “no change,” or “worsened” based on changes from the baseline JDA severity index scores and components, as presented in [Table 8-6](#).

Table 8–6: Global Improvement Score

	Change in JDA Severity Classification Score		Other criteria
Very much improved	Reduction by ≥ 3 points	or	Clear or almost clear of signs of generalized pustular PSO
Much improved	Reduction of 1 or 2 points	or	At least 1 of the following: Erythema area with pustules (%) reduced by $\leq 30\%$ compared to Baseline Clinically meaningful improvement in at least 2 other components of the JDA Severity Index for generalized pustular PSO (erythema area, edema area, WBC, CRP, albumin)
Minimally improved	0 points (no change)	and	At least 1 of the following: Erythema area with pustules (%) reduced by $\leq 20\%$ compared to Baseline Clinically meaningful improvement in at least 1 other component of the JDA Severity Index for generalized pustular PSO (erythema area, edema area, WBC, CRP, albumin)
No change	0 points (no change)	and	Not meeting the other criteria of minimally improved
Worsened	$\geq +1$ point	-	Not applicable

Frequency tables by visit and by randomized treatment group for the Initial Period as well as by visit and by maintenance treatment group for the Maintenance Period will be provided for the results of the Global Improvement Score based on the GPPS on Observed case data and NRI imputed data.

Within NRI imputation, missing values are imputed with the category “No Change”.

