Two Phase 2 clinical studies have been completed assessing CZP in adult subjects with moderate to severe chronic plaque PSO. The first study, C87040, demonstrated that CZP in doses of 200mg Q2W (with a 400mg loading dose at Week 0) or 400mg Q2W improved the signs and symptoms of PSO as measured by PASI75 and Physician's Global Assessment (PGA), with up to 82.8% of subjects responding to treatment (PASI75) at the higher dose. A second Phase 2 study, C87044, provided safety and efficacy data on the withdrawal and retreatment of subjects who responded to their initial treatment course in study C87040.

Based on the positive safety and efficacy results from Phase 2, and the need for new treatment options for PSO, three Phase 3 studies are ongoing (PS0002, PS0003, and PS0005). These Phase 3 studies will study the efficacy of CZP in subjects with moderate to severe plaque PSO compared to PBO treatment (PS0002 and PS0005) and to an active comparator (etanercept) and PBO treatment (PS0003). The proposed study in Japan will study the efficacy of CZP in subjects with moderate to severe plaque PSO compared to PBO treatment, and an exploratory evaluation of this study will be performed in regard to efficacy on joint symptoms in patients with PsA who are enrolled having plaque eruptions and joint symptoms.

In addition, the efficacy and safety of CZP in Japanese patients with generalized pustular PSO and erythrodermic PSO will be also assessed. As described above, plaque PSO is the most common form, but more severe variants include generalized pustular PSO and erythrodermic PSO. Patients with generalized pustular PSO or erythrodermic PSO are often refractory to currently available therapies, and there is a need for effective treatment for these types of PSO. Certolizumab pegol is a biological product that may be desirable to develop as a drug for PSO including these types of PSO. However, considering the very small population, the evaluation of generalized pustular PSO and erythrodermic PSO in a double-blind manner is not possible. Consequently, the efficacy and safety of CZP in these populations will be evaluated in an open-label design in an exploratory fashion.

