5.1.2 Study design for subjects with generalized pustular PSO or erythrodermic PSO

5.1.2.1 Period 1: Screening

The Screening Period of 2 to 5 weeks will be used to confirm eligibility and obtain laboratory data.

5.1.2.2 Period 2: Week 0 to Week 16

At least 10 subjects in the cohort with generalized pustular PSO or erythrodermic PSO will be allocated in a 1:1 ratio to the following open-label study treatments:

- CZP 400mg (n ≥5): CZP administered sc at the dose of CZP 400mg Q2W
- CZP 200mg (n ≥5): CZP administered sc at the dose of CZP 400mg at Weeks 0, 2, and 4, followed by CZP 200mg Q2W (starting at Week 6)

5.1.2.3 Period 3: Week 16 to Week 52

The treatment received in Period 3 will be based on the initial study treatment and on response to open-label treatment at Week 16:

- Subjects achieving a “much improved” or “very much improved” in the Global Improvement Score (for subjects with generalized pustular PSO) or a PASI50 response (for subjects with erythrodermic PSO) will continue to receive the same treatment as randomized.
- Subjects in the CZP 200mg Q2W group who are not in response (not achieving “much improved” or “very much improved” in the Global Improvement Score [for subjects with generalized pustular PSO] or a PASI50 response [for subjects with erythrodermic PSO]) will be allowed to have their dose increased to CZP 400mg Q2W, at the discretion of the Investigator. Subjects randomized to CZP 400mg Q2W will continue to receive CZP 400mg Q2W at the discretion of the Investigator. If, in the opinion of the Investigator, the subject is not receiving benefit at the 400mg Q2W dose, the subject could be withdrawn from the study. Per the Withdrawal Criteria (Section 6.3), subjects who develop an aggravation of the primary disease or concomitant disease with hospitalization in the opinion of the Investigator must be withdrawn from the study.

5.1.2.4 Period 4: Safety Follow-up: Week 52 to Week 60

All subjects, including those withdrawn from study treatment, will have a Safety Follow-Up Visit 10 weeks after their final dose of study medication.

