8.3.19 JDA Severity Index Score for generalized pustular PSO

The JDA severity index score for generalized pustular PSO consists of area of erythema with pustules, area of erythema (total), area of edema, fever, WBC count, CRP, and serum albumin, as displayed in [Table 8–7](#).

The total score of JDA severity index for generalized pustular PSO is assigned a score of 0 to 17 (0=best, 17=worst).

Descriptive statistics for the absolute values and changes vs. Baseline will be provided by visit and by randomized treatment group for the Initial Period and by maintenance treatment group for the Maintenance Period based on GPPS on Observed case data and LOCF imputed data.

Table 8–7: JDA severity index or generalized pustular PSO

Severity classification	Mild	Moderate	Severe
A + B (combined scores)	0 to 6	7 to 10	11 to 17

Table 8–7: JDA severity index or generalized pustular PSO

A. Skin symptoms (total scores: 0 to 9)				
Scores	3	2	1	0
Erythematous area (BSA %)	≥75	≥25, <75	<25	0
Erythematous area with pustule (BSA %)	≥50	≥10, <50	<10	0
Edematous area (BSA %)	≥50	≥10, <50	<10	0
B. Systemic symptoms and laboratory findings (total scores: 0 to 8)				
Scores	2	1	0	
Fever (°C)	≥38.5	≥37.0, <38.5	<37.0	
WBC count (/μL)	≥15,000	≥10,000, <15,000	<10,000	
CRP (mg/dL)	≥7.0	≥0.3, <7.0	<0.3	
Serum albumin (g/dL)	<3.0	≥3.0, <3.8	≥3.8	

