9.4 Relationship between immunogenicity and efficacy variables

The results of the interim analysis demonstrated that almost all subjects showed TE-ADA positivity regardless of treatments and psoriatic subgroups and the relationship between immunogenicity and efficacy variables could not be investigated sufficiently using the summaries of Anti-CZP Antibody Titer. The subjects who had TE-ADA positivity showed various ADA titer values, therefore, the relationship between immunogenicity and efficacy variables will be investigated using the ADA titer values.

The definition of Maximum ADA titers is the same as in Section 9.3.

Maximum ADA titers are classified based on measured values and aggregated in the following categories.

- Low: maximum ADA titer \leq 1024
- High: maximum ADA titer $>$ 1024

The constitution of the treatment group of Week 16 conforms to the treatment group of Initial Period and the constitution of the treatment group of Week 24/Week 52 conforms to the treatment group of Combined Initial and Maintenance Period of Section 9.2.4.

For the efficacy variable, frequency counting is performed on Maximum ADA titer and Maximum ADA titer category for each analysis set and treatment group.

- Subjects with plaque PSO
 - Population: plaque PSO
Analysis Set: Pharmacokinetics Per-Protocol Set
Efficacy variables: PASI75 (Non-Responder Rate), PASI90 (Non-Responder Rate), PGA (Non-Responder Rate)
 - Population: PsA Subjects with 3 or more tender joints and 3 or more swollen joints at Baseline)
Analysis Set: Pharmacokinetics Per-Protocol Set (PsAS (Subjects with 3 or more tender joints and 3 or more swollen joints at Baseline))
Efficacy variable: ACR20 (Non-Responder Rate)
- Subjects with erythrodermic PSO or generalized pustular PSO
 - Population: Erythrodermic PSO
Analysis Set: Cohort Pharmacokinetics Set (Erythrodermic PSO Set)
Efficacy variables: PASI75 (Non-Responder Rate), PASI90 (Non-Responder Rate), PGA (Non-Responder Rate)
 - Population: Generalized Pustular PSO
Analysis Set: Cohort Pharmacokinetics Set (Generalized Pustular PSO Set)
Efficacy variable: Global Improvement Score (Non-Responder Rate)

Analysis Considerations

Data at the EWD visit will be summarized separately from the scheduled visits.

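### The pustular-area thresholds in the Global Improvement Score are printed the wrong way round: as written, a 4% fall rates *much improved* and a 67% fall can rate *no change*

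*SAP*

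**What the plan says.** The Investigator assigns one of five categories from a table that appears in both documents: Protocol 9.8.2 (Table 9-3) and SAP 8.3.18 (Table 8-6).

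- *Very much improved*: a JDA fall of at least 3 points, or skin clear or almost clear.
- *Much improved*: "Reduction of 1 or 2 points" in the JDA score, or at least one of two alternatives. The first is the area criterion, "Erythema area with pustules (%) reduced by" a stated percentage, with the threshold printed as "reduced by $\leq 30\%$ compared to Baseline". The second is clinically meaningful improvement in at least two other JDA components.
- *Minimally improved*: no JDA change, and either an area reduction of at most 20% or "Clinically meaningful improvement in at least 1 other component of the JDA Severity Index for generalized pustular PSO".
- *No change*: no JDA change, and none of the *minimally improved* criteria met.
- *Worsened*: a JDA rise of 1 point or more; the column of other criteria is marked as not applying.

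The score is used in three places. SAP 8.3.18 tabulates it by visit. SAP 9.4 analyses it by maximum ADA titer: "Efficacy variable: Global Improvement Score (Non-Responder Rate". Protocol 5.1.2.3 and SAP 2.3.2.3 define Week 16 response as one of the top two categories "in the Global Improvement Score (for subjects with generalized pustular PSO) or a PASI50 response"; 200 mg subjects who do not respond may be raised to 400 mg Q2W at the Investigator's discretion.

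**The concern.** An improvement scale should ask for at least a given reduction, with a larger reduction for the better category. Here the two area criteria cap the reduction instead, so a trivial fall qualifies for a good category and a large fall is shut out.

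A text-extraction fault is unlikely. Both documents print the same two signs, and in the same tables the 3-point JDA criterion carries the correct direction. No other text corrects the signs. The SAP's Amendment 2 summary (12.2) records a revision to 8.3.18, but only to the category used for missing data.

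Investigators rate from this table. If one site applies it literally and another silently reverses the signs, the same patient gets different ratings, and possibly a different dose decision at Week 16.

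**Working it through.** There is no plan figure to reproduce; the check applies the printed rule and then the rule with the signs reversed.

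**Inputs.** Category rules from SAP Table 8-6. Area bands from SAP Table 8-7, row "Erythematous area with pustule (BSA" %): 50 or more scores 3; 10 to below 50 scores 2; below 10 scores 1; zero scores 0. A responder is *much improved* or *very much improved* (Protocol 5.1.2.3).

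**Conventions.** Reduction r = 100 × (Baseline area − visit area) / Baseline area. All other JDA components stay at Baseline, the skin is not clear or almost clear, and the best row met is taken. The last convention is needed because the documents state no precedence.

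**Worked cases**, all inside the 10 to below 50% band, so the JDA score does not move:

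| Area, % BSA | r | As printed | Signs reversed |
|---|---|---|---|
| 45 to 43 | 2/45 = 4.4% | much improved | no change |
| 45 to 34 | 11/45 = 24.4% | much improved | minimally improved |
| 45 to 15 | 30/45 = 66.7% | no change | much improved |
| 49 to 10 | 39/49 = 79.6% | no change | much improved |

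Any fall of at most 20% is also at most 30%. As printed, the *minimally improved* area criterion can therefore never decide the best row.

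**All whole-percent pairs.** Take Baseline b = 1 to 100 and visit f = 1 to b − 1, both in the same band: 36 (below 10) + 780 (10 to below 50) + 1,275 (50 or more) = 2,091 pairs.

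| Rule | Much improved | Minimally improved | No change |
|---|---|---|---|
| As printed | 1,305 | 0 | 786 |
| At least 30% / at least 20% | 792 | 411 | 888 |

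Cross-classifying printed against reversed: much/no change 888, much/minimal 411, no change/much 786, much/much 6. Responder status differs in 888 + 411 + 786 = 2,085 pairs and agrees in the 6 where r is exactly 30%. With reversed signs the largest fall still rated *no change* is 19.8%, and the categories are ordered.

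**Effect of one reclassified subject.** A responder rate moves by 100/n points. The documents do not give n for pustular subjects. Assuming 3, 5 or 10, the shift is 33.3, 20.0 or 10.0 points.

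**Precedence, a separate gap.** The *much improved* alternatives are joined by *or*. A subject whose area criterion is met while the JDA score has risen by 1 point satisfies both *much improved* and *worsened*. This would remain after the signs are corrected.

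**The case against.** Several objections are fair, but none removes the inversion.

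- *The 4% example depends on taking the best row.* True: a 4.4% fall meets both the 30% and the 20% caps, and no precedence is stated. But the alternative needs an equally unstated rule, and the large-fall example does not depend on precedence.
- *The percentage could mean BSA points.* Then 45 to 15% is exactly 30 points and is *much improved*, so that example fails. But 49 to 10% is 39 points and is still *no change*. A reduction relative to Baseline is the more natural reading; the correction should say which is meant.
- *The pair count restates the inversion.* Largely so. Reversing a sign flips nearly every pair by construction, and in practice a changed JDA score or improvement in one of five other components will often decide the row. The counts describe the rule, not patients.
- *The 100/n denominators are not those of every table.* SAP 3.6.2 reserves pooled cohort columns for safety data, so by-visit tables use smaller groups. SAP 9.4, however, takes its groups from 9.2.4, which includes a pooled CZP column. The figures are illustrations only.
- *The worsened row may be meant to override.* That is one fair reading of its not-applicable entry, but the text does not say so.
- *The score is rated, not programmed, and the cohort is exploratory.* Correcting Table 8-6 alone would not change recorded ratings, and the JDA score and CGI-I are analysed separately without these thresholds. Protocol section 2 says efficacy and safety in these populations "will be evaluated in an open-label design in an exploratory fashion". This limits the reach of the error; it does not make the table right.

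**Conclusion.** The concern holds. Both area thresholds in both tables have the wrong sign, and no rule settles overlapping rows. The worked cases and counts assume relative change, all other components held at Baseline and the best row taken; the inversion itself survives a reading in BSA points. That the intended rule is at least 30% and at least 20% is an inference, because the documents do not state it.

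This should be fixed: it is a wrong threshold in a listed efficacy variable that also defines Week 16 response. Its reach is limited to the pustular cohort, which has descriptive tables only and no primary or secondary efficacy variable. The documents do not show that any subject was misrated.

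**What to change.** In SAP Table 8-6 and Protocol Table 9-3:

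1. Change both area criteria to minimum reductions (at least 30% for *much improved*, at least 20% for *minimally improved*), with the values confirmed by the sponsor, and say that the reduction is relative to the Baseline area if that is what is meant.
2. Add one sentence on which row prevails when several are met, including when the area criterion is met but the JDA score has risen. That choice is the sponsor's.
3. Keep the Investigator rating. Do not replace it with an algorithm, because clinically meaningful improvement and clear or almost clear skin have no numeric definition.
4. Compare recorded categories with recorded areas and JDA scores, and report any that disagree with the corrected table.

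The cost is two sign changes and a short clarification per table, plus one listing. The Protocol edit may need an amendment under Protocol 15.5. No new data collection is needed, provided the area percentages were recorded and not only the banded scores; the documents do not show which.

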6.2.3 Exclusion criteria for subjects with generalized pustular PSO or erythrodermic PSO

Psoriasis exclusion criteria

27. Subject has a total score on the JDA severity index for generalized pustular PSO ≥ 14 at Baseline if subjects have a diagnosis of generalized pustular PSO.

28. Subject has a differential diagnosis of the erythroderma (eg, erythroderma caused by lymphoma or drug eruption) other than erythrodermic PSO.

Prior medications exclusions

29. Subject with a primary failure to any prior biologic therapy (primary failure defined as no response within the first 12 weeks of treatment with the biologic).

30. Subject used the following medications and therapies in the manner as detailed by the exclusion criteria in Table 6–2:

Table 6–2: Exclusions for prior treatments for subjects with generalized pustular PSO or erythrodermic PSO

Drug class	Dose	Exclusion criteria relative to Baseline Visit
Systemic treatment (nonbiological) ^a Phototherapy or chemophototherapy Granulocyte and monocyte adsorption apheresis	-	4 weeks for phototherapy or chemophototherapy 1 week for granulocyte and monocyte adsorption apheresis
Anti-TNFs Infliximab (including biosimilar) Adalimumab Etanercept Golimumab	Any dose	12 weeks for infliximab (including biosimilar), adalimumab, and golimumab 4 weeks for etanercept
Other biologicals and other systemic therapies Ustekinumab Secukinumab Brodalumab Ixekizumab Rituximab	Any dose	2 years for rituximab 24 weeks for ustekinumab, secukinumab, brodalumab and ixekizumab
Any other antipsoriatic agent (systemic) under investigation (or approved after the protocol is approved)	Any dose	24 weeks
Topical agents Antipsoriatic agent (topical) under investigation (or approved after the protocol is approved)	Any dose	4 weeks

^a The use of systemic retinoids, systemic immunosuppressants agents (eg: methotrexate, cyclosporine, azathioprine) and/or systemic corticosteroids (at a daily dose ≤10 mg/day of prednisone or its equivalent) are allowed provided the patient has been using such medication(s) since before starting the study. Dose reduction of these drugs is allowed as well; however, dose increase after dose reduction is limited to the level at the start of the study.

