6.3 Withdrawal criteria

Subjects are free to withdraw from the study at any time, without prejudice to their continued care.

Subjects should be withdrawn from the study if any of the following events occur:

1. Subject develops an illness that would interfere with his/her continued participation.
2. Subject is noncompliant with the study procedures or medications in the opinion of the Investigator.
3. Subject considered as having either a suspected new latent or who develop active TB or NTMB infection during the study (including but not limited to, conversion demonstrated by IGRA or other diagnostic means) must be immediately discontinued from study medication, and an Early Termination Visit must be scheduled as soon as possible, but not later than the next regular visit.

Confirmed active TB is a serious adverse event (SAE) and must be captured on an SAE report form and provided to the Sponsor in accordance with SAE reporting requirements. As with all SAEs, periodic follow-up reports should be completed as per protocol requirements until such time as the TB infection resolves.

Subjects who prematurely discontinue treatment for latent TB, or, in the opinion of the Investigator or Sponsor, are noncompliant with anti-TB therapy must discontinue further use of study medication and be immediately withdrawn.

4. There is confirmation of a positive HBV-DNA assay during the study period, subject with positive HBc antibody and/or HBs antibody at Screening. Appropriate actions such as administration of a nucleic acid analog should be taken after prompt consultation with a hepatologist.
5. Subjects developing aggravation of the primary disease or concomitant disease with hospitalization in the opinion of the Investigator.
6. Subjects with generalized pustular PSO developing a total score on the JDA Severity Index for Generalized Pustular PSO ≥ 14 at any post-Baseline visit.
7. Subject withdraws his/her consent.
8. There is confirmation of a subject pregnancy during the study, as evidenced by a positive pregnancy test.
9. The Sponsor or a regulatory agency requests withdrawal of the subject.
10. Subjects develops guttate PSO.

Once withdrawn from study treatment, subjects must return for the Early Withdrawal Visit and complete all Early Withdrawal assessments, and complete a final Safety Follow-Up Visit 10 weeks after the last dose of study medication.

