8.30 Withdrawal Visit

Subjects will have the following procedures performed/recorded:

- Blood pressure
- 12-lead ECG
- Weight
- Hematology, biochemistry, and urine for clinical laboratory values, including beta-D-glucan and sialylated carbohydrate antigen KL-6
- Urine pregnancy test for women of childbearing potential
- Plasma for PK and immunogenicity samples
- Physical examination, including evaluation for signs and symptoms of TB
- Chest x-ray
- IGRA
- Subject TB questionnaire
- PASI (will not be performed in subjects with generalized pustular PSO)
- PGA (will not be performed in subjects with generalized pustular PSO)
- Itch Numeric Rating Scale
- DLQI
- BSA affected by PSO (will not be performed in subjects with generalized pustular PSO)
- mNAPSI (for subjects with psoriatic nail disease)
- Subject PsA assessments (HAQ-DI, Patient's Assessment of Arthritis Pain, and Patient's Global Assessment of Disease Activity for subjects with PsA)
- Physician PsA assessments (swollen and tender joint counts and Physician's Global Assessment of Disease Activity for subjects with PsA)
- Pustular and erythrodermic PSO assessments (Global Improvement Score, JDA Severity Index, and CGI-I for subjects with generalized pustular PSO or CGI-I for subjects with erythrodermic PSO)
- Medical procedures

- Concomitant medication
- AEs
- IRT information

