3.2.4 Mapping of assessments performed at Early Discontinuation Visit

Study assessments at an early withdrawal visit will be assigned to the next scheduled site visit following the last visit where assessments were available regardless of if the actual early withdrawal visit date matches another scheduled visit date. The early withdrawal visit re-mapping is not done for pharmacokinetics and anti-CZP antibodies.

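### The NRI tables for CGI-I and Global Improvement Score show 'No Change' at later visits for cohort subjects who were withdrawn because their psoriasis worsened

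*SAP*

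**What the plan says.** **Imputation.** SAP 8.3.17 (CGI-I) and 8.3.18 (Global Improvement Score) plan frequency tables over all categories, on observed-case and on NRI data. For the NRI version both sections say: "Within NRI imputation, missing values are imputed with the category" *No Change*. Neither makes an exception for the reason for missingness. SAP 8.3.19 imputes the JDA score itself by LOCF.

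**Category definitions.** The Global Improvement Score is "based on changes from the baseline JDA severity index scores and components". In SAP Table 8-6, *No change* needs a change of 0 points and *Worsened* needs +1 or more. CGI-I is the investigator's four-category rating against Baseline psoriasis findings, and *worsened* is one of the four.

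**Withdrawal.** Protocol 6.3, criterion 5: "Subjects developing aggravation of the primary disease or concomitant disease with hospitalization in the opinion of the Investigator". Protocol 5.1.2.3 makes this mandatory for the cohort. Criterion 6: "Subjects with generalized pustular PSO developing a total score on the JDA Severity Index for Generalized Pustular PSO" of 14 or more at any visit after Baseline. At entry, exclusion criterion 27 (Protocol 6.2.3) reads: "Subject has a total score on the JDA severity index for generalized pustular PSO" of 14 or more at Baseline.

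**Data at withdrawal.** Protocol 8.30 lists "Pustular and erythrodermic PSO assessments (Global Improvement Score, JDA Severity Index, and CGI-I for subjects with generalized pustular PSO", and CGI-I for erythrodermic subjects. SAP 3.2.4 adds: "Study assessments at an early withdrawal visit will be assigned to the next scheduled site visit following the last visit" that has data.

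**The concern.** *No Change* is a cautious value when the output is a responder count. Here the output is a full frequency table that includes a category below *No Change*, and the rule is favourable at that end of the scale.

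The subjects most affected are those the protocol removes because the disease got worse. Their last known state is worse than Baseline, yet the NRI table places them back at Baseline level for the rest of follow-up. In a cohort this small the category counts are the efficacy result. The protocol's introduction describes both diseases as potentially fatal, so the lower end of the table is the part a reader will look at.

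**Working it through.** The plan gives no figure for this point (Protocol 14.8.2 has no calculated sample size for the cohort), so there is nothing to reproduce. Four checks follow.

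**1. Smallest JDA change at a criterion-6 withdrawal.** The total is a whole number from 0 to 17. An eligible subject has Baseline of at most 13, and the criterion needs at least 14. Minimum change = 14 − 13 = +1. That meets the *Worsened* row and cannot meet the *No change* row, which needs 0. Table 8-6 also has alternative routes into the improved categories and gives no order of precedence, but none of them leads to *No change*.

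For CGI-I the link is expected rather than definitional, because CGI-I is a rating and is not computed from JDA. For criterion 5 it depends on which disease was aggravated.

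**2. The two imputed tables side by side.** Take a subject with Baseline JDA 13 who is withdrawn at 14. At each later visit the LOCF JDA table shows +1, and the NRI Global Improvement Score table shows *No Change*. The second score is built on the first, so the tables contradict each other. SAP 4.2 limits LOCF to scheduled assessments, so the contradiction arises when the JDA value of 14 or more counts as scheduled.

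**3. Visits affected.** The scores are scheduled at Weeks 2, 4, 8, 12, 16, 20, 24, 28, 32, 36, 40, 44, 48 and 52, which is 14 visits. Site visits are every 2 weeks. Read literally, SAP 3.2.4 can therefore place the withdrawal record in a week with no scheduled score.

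| Last attended visit | Later scheduled scores | Left as *No Change* if mapped to next scheduled score | Left as *No Change* if mapped to next site visit |
|---|---|---|---|
| Week 4 | 12 | 11 (maps to Week 8) | 12 (maps to Week 6) |
| Week 16 | 9 | 8 (maps to Week 20) | 9 (maps to Week 18) |
| Week 40 | 3 | 2 (maps to Week 44) | 3 (maps to Week 42) |

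These counts assume the subject stays in the table to Week 52. SAP 3.6.2 does not say whether cohort subjects withdrawn before Week 16 enter the Maintenance columns. If they do not, the Week 4 row falls to 2 or 3 visits (Weeks 12 and 16, with or without Week 8).

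**4. Size per subject.** Shift at each affected visit = 100/n percentage points. The cohort is at least 10, allocated 1:1, so at least 5 per arm with both diseases combined. SAP 3.6.2 splits the Initial Period by disease and dose into four columns, an average of 10/4 = 2.5 at the minimum cohort size. Actual column sizes are not given, so these are assumed:

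- n=5: 100/5 = 20 points
- n=3: 100/3 = 33 points
- n=2: 100/2 = 50 points

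The documents give no expected number of such withdrawals, so one is assumed.

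**The case against.** A reader might infer that the worst outcomes vanish from both versions of the table. The documents do not support that.

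- **The worsening is recorded.** The withdrawal visit collects these scores. A criterion-6 trigger found at a scheduled visit comes with a Global Improvement Score at that same visit.
- **Observed-case tables do not impute.** SAP 3.1 keeps missing observations in categorical summaries, so a withdrawn subject should appear there as missing and is not dropped.
- **The events are reported elsewhere.** Disposition with reasons covers the randomized cohort (SAP 5.1). Hospitalization makes an adverse event serious (Protocol 12.1.1.2). Serious events, events leading to discontinuation and deaths are tabulated for the cohort (SAP 10.2).
- **Response is untouched.** Global Improvement Score response means *much improved* or better (Protocol 5.1.2.3). *No Change* and *Worsened* are both non-response.
- **Little depends on it.** The cohort has no primary or secondary efficacy variable and is described as exploratory.

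A reader might also infer that every withdrawal for aggravation should count as *Worsened*. That is not supported either: criterion 5 includes concomitant disease, and both scores rate psoriasis.

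All of this stands and limits the point. Status after withdrawal is also unobserved, so *Worsened* at later visits is an assumption. But *No Change* is an assumption too, and for criterion-6 subjects it contradicts the last known score.

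**Conclusion.** The point holds in a narrow form. In the NRI frequency tables of SAP 8.3.17 and 8.3.18, visits after withdrawal become *No Change* even when withdrawal was for a JDA total of 14 or more, or for hospitalised aggravation of the psoriasis itself. For the Global Improvement Score after a criterion-6 withdrawal this follows from the plan's own thresholds. For CGI-I, and for criterion 5, it is the likely but not the certain category.

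The shortfall in *Worsened* is relative to last known status, not to a known later outcome. One such subject shifts a column by 20 to 50 points at each later visit for assumed column sizes of 5 down to 2. No responder rate and no confirmatory result is affected.

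**What to change.** In SAP 8.3.17 and 8.3.18, state that in the NRI tables visits after a criterion-6 withdrawal, or after a criterion-5 withdrawal where the aggravated disease is the psoriasis itself, are shown as *Worsened* or in a separate row for withdrawal due to worsening. Other missing values stay *No Change*. The separate row has the advantage of not asserting an unobserved category.

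For these scores, also state in SAP 3.2.4 that the withdrawal visit maps to the next visit at which they are scheduled, and apply the same mapping to the JDA score so that the NRI and LOCF tables agree.

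This takes about two sentences and no new data, and it changes nothing in subject management. The price is slightly less favourable tables and a later status that is assumed rather than observed.
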